## 12.6 Multiplicity

No adjustment for multiplicity will be made since there is a single primary comparison between the 5% benzocaine condom versus standard NRL condom.

## 12.7 Sample size and statistical power

In a publication titled "A Multinational Population Survey of Intravaginal Ejaculation Latency Time (Waldinger et al., 2005)", 500 couples were studied in a non-interventional setting over a 4-week period. The mean IELT was 8 minutes (SD = 7.1). Assuming this will be representative of the IELT of men using the standard NRL condom, and that the correlation between repeated measurements within the same subject in the 3 periods of the crossover trial will be 0.5, the table below shows the number of subjects required to detect a clinically meaningful difference of 2 minutes in mean IELT between the Test Condom A (5% Benzocaine paste) and the Control NRL Condom at 90% power, with a significance level of 5% using a two-sided paired t-test.

IELT (mins)		Number of Subjects	
Control NRL Condom	Test Condom A (5% Benzocaine paste)	Number to complete	Number randomised (10% drop out)
8	10	135	150

A sample size of 135 subjects will be sufficient to detect a difference of 2 minutes in mean IELT between the Test Condom A and the Control NRL Condom. Allowing for a dropout rate of 10%, 150 subjects will be randomized.

A 2 minute difference in IELT is considered clinically meaningful based on previous studies identified in the published literature. Shabsigh et al (2019) conducted a randomised controlled trial of topical 4% benzocaine wipes for the management of PE defined as self-reported poor control over ejaculation and an IELT of 2 minutes or less. Results showed a statistically significant increase in mean IELT of 164.80 ( $\pm 11.40$  SE) seconds after 1 month of treatment compared to placebo (110.10 s  $\pm 9.90$  SE). The clinical benefit of a difference in IELT of 1 minute or larger compared to placebo is demonstrated via a patient reported outcome known as the Index of Premature Ejaculation (IPE) whereby the men in the treatment group reported significantly higher sexual satisfaction and greater improvement in distress related to intercourse. For the purposes of relevance to the target population, a larger 2-minute difference in IELT has been selected as the relevant effect for this clinical investigation based on the subjects being healthy adult men as opposed to only men with PE (IELT <2 minutes).

## 12.8 Randomisation

### Randomisation details

Subjects will be allocated to a condom use regime (one of six treatment sequences in a fixed block size of 6 with 34 blocks) according to a computer-generated randomization schedule produced by the CRO. The blocks are each balanced in the ratio 1:1:1.

A randomization schedule will be generated for 204 kits to account for dropouts, overage, replacement and additional randomization codes for IMSU retention samples (which will be retained at Reckitt).

Randomized subjects will be numbered sequentially. The possible range of randomization numbers is accordingly between 1 and 204.

Randomization will be done with SAS software version 9.4-TS-1M7 or higher.

### Overview

- Total number of randomization numbers is **204**
- 150 subjects to be randomised + 42 (28% overage) = **192** randomisation numbers with 34 blocks each of size 6
- **12** randomization numbers for IMSU retention (2 complete blocks)
- **192 + 12 = 204**

### Information for replacement

Kits will be numbered sequentially. The kit numbers correspond to the subjects' randomisation numbers, as given in the randomization list. Additionally, to this randomisation list, a second list will be generated, which assigns the kit number to the corresponding treatment regimen (n=6 different treatment sequences).

This second list will only contain a treatment regime identifier code (numbers 1 to 6) and will not state the exact sequence of the test products. This list will remain with the Site throughout the study and will be available to the site staff in the case that they need to supply a subject with a replacement kit. This will ensure that same regime is continued by the affected subject, but also does not allow the site staff to draw any conclusions about the exact treatment sequence as they only have access to the treatment regime identifier.

In the case that a kit or single carton is damaged, the site staff will replace the whole kit or carton, respectively. If a single condom packaging is damaged the whole carton is replaced. The replacement will be recorded in the eCRF via a remark. The damaged kit/carton is photographed and stored at the site until shipment to the sponsor together with the unused investigational products (see CIP section 5.9).

A replaced kit cannot be used for another subject.

## 12.9 Interim analyses

No interim analysis is planned.

## 12.10 Subgroup analyses

Not applicable.

## 12.11 Adjustment for covariates

Not applicable.

## 12.12 Confidence intervals

Confidence intervals (CI) for means are given where suitable. They are computed two-sided based on asymptotic normality at a confidence level of 95 % = 100 · (1 - α) %, if not stated otherwise:

$$CI = \mu \pm c \cdot \frac{\sigma}{\sqrt{n}}$$

for  $\mu$  = Sample mean for the respective variable

$c = t_{\alpha, 1-\alpha/2, n-1}$  Percentile of the t distribution

$\sigma$  = Sample standard deviation for the respective variable

$n$  = Sample size

Confidence intervals (CI) for odds ratio are given where suitable. They are computed two-sided based on asymptotic normality at a confidence level of 95 % = 100 · (1 - α) %:

This calculator uses the following formulae to calculate the odds ratio (or) and its confidence interval. or = a · d / b · c, where:

- a is the number of times both A and B are present,
- b is the number of times A is present, but B is absent,
- c is the number of times A is absent, but B is present,
- d is the number of times both A and B are negative.

Contingency table	A	1	0	Marginal sum
B				
1		a	b	a+b
0		c	d	c+d
Marginal sum		a+c	b+d	a+b+c+d

To calculate the confidence interval, we use the log odds ratio

$$\log(or) = \log(a \cdot d / b \cdot c)$$

with its standard error

$$SE(\log(or)) = \sqrt{\frac{1}{a} + \frac{1}{b} + \frac{1}{c} + \frac{1}{d}}$$

The confidence interval is calculated as:

$$CI = \exp(\log(or) \pm Z_{\alpha/2} \cdot \sqrt{\frac{1}{a} + \frac{1}{b} + \frac{1}{c} + \frac{1}{d}})$$

where  $Z_{\alpha/2}$  is the critical value of the normal distribution at  $\alpha/2$  (e.g., for a confidence level of 95%, the type I error is,  $\alpha = 0.05$  and its critical z-value is  $Z = 1.96$ ).

Note: The logarithms included in the formulae above are natural logarithms, i.e., log base e, sometimes denoted as  $\ln()$ .

Confidence Intervals for Wilcoxon signed rank test are calculated according to Hodges-Lehmann. This is done according to the following method:

Let  $[\lambda_*, \lambda^*]$  be the exact  $100 \cdot (1 - \alpha)\%$  confidence interval for the median difference. Let  $M = \frac{N(N+1)}{2}$

and let  $A_{[1]} \leq A_{[2]} \leq A_{[...]} \leq A_{[M]}$  be the  $M$  averages,  $\frac{(d_i + d_j)}{2}$  for all  $i \leq j$ , sorted in ascending order.

The lower confidence interval is formed by setting  $\lambda_* = A_{[i]}$  where  $[i] = 1 + t_*$  where  $t_*$  rounds down  $t_*$  to the nearest integer.

The upper confidence interval is formed by setting  $\lambda^* = A_{[i]}$  where  $[i] = t^*$  where  $t^*$  rounds up  $t^*$  to the nearest integer.

$t_*$  is determined by finding a value for  $t_*$  so that the formula satisfies the following condition:

$$\Phi \left( \frac{t_* - \frac{N \cdot (N+1)}{4}}{\sqrt{\frac{N \cdot (N+1) \cdot (2N+1)}{24}}} \right) = \frac{\alpha}{2}$$

$t^*$  is determined by finding a value for  $t^*$  so that the formula satisfies the following condition:

$$1 - \Phi \left( \frac{t^* - \frac{N \cdot (N+1)}{4}}{\sqrt{\frac{N \cdot (N+1) \cdot (2N+1)}{24}}} \right) = \frac{\alpha}{2}$$

The confidence intervals for the proportion values are calculated according to the Wilson Score method. The following calculation method is used for this purpose:

$$CI = \frac{1}{1 + \frac{c^2}{n}} \cdot \left( \hat{p} + \frac{c^2}{2n} \pm c \cdot \sqrt{\frac{\hat{p} \cdot (1 - \hat{p})}{n} + \frac{c^2}{4n}} \right).$$

For  $c = \phi^{-1} \cdot (1 - \frac{\alpha}{2})$  where  $\frac{\alpha}{2}$  is the two sided error level and  $\phi^{-1}$  denotes the quantile function of the standard normal distribution, i.e. the inverse function of its distribution function  $\Phi$ .

$\hat{p}$  denotes the estimated proportion value.

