**For secondary endpoints**

All secondary endpoints will be evaluated based on comparing the 5% and 3% benzocaine condoms with the standard NRL condom. No adjustment for multiplicity is planned for the secondary endpoints, and so p-values will be interpreted with appropriate consideration of Type I error.

The secondary endpoints of the investigation are:

Change from baseline in IELT with the 3% Benzocaine condom compared to the standard NRL Condom, over a 4-week assessment period.

Proportion of subjects who achieve an increase of 2, 3, 4 mins from baseline in IELT in the 5% and 3% benzocaine condoms compared to the standard NRL Condom.

- The change from baseline IELT with the 3% benzocaine condom compared to the standard NRL condom will be evaluated using the same linear mixed model as for the primary endpoint. The difference in least square means and associated 95% CI will be calculated, with a p-value to assess statistical significance.
- The proportion of subjects who achieve an increase of 2, 3 or 4 mins from baseline in IELT (calculated from the mean across all intercourse episodes within a period) will be calculated

for each condom type. The proportion achieving an increase of 2, 3 or 4 mins will be compared for the 5% and 3% benzocaine condoms versus the standard NRL condom using a GLMM with marginal means under the assumption that the mean of the outcome variable (1=success or 0=failure) follows a binomial distribution. Factors in the model will include fixed effects for treatment and period, and baseline IELT as a covariate. Subject will be included as a random effect. Comparison between the 5% and 3% Benzocaine condoms with the standard NRL condom will be expressed as an odds ratio, with an associated 95% CI and p-value.

A measure of Patient Global Impression of Change (PGIC) at the end of each 4-week assessment period, in subjects using the 5% and 3% benzocaine condoms compared to the standard NRL Condom.

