95 % confidence intervals	
For the analysis of the IELT with the 5% Benzocaine condom versus the standard NRL condom, 95% confidence intervals and an associated p-value are calculated. The calculation is done for each estimator of each time point separately for each condom group.
 
For the proportion of subjects in the total collective who achieved increase of 2, 3, 4 mins, comparison between the 5% and 3% Benzocaine condoms with the standard NRL condom will be expressed as an odds ratio, with an associated 95% CI.
 
For the analysis of PGIC, the comparison between the 5% and 3% Benzocaine condoms with the standard NRL condom will be expressed as an odds ratio, with an associated 95% CI.
 
For the descriptive analysis of EMSEX pleasure scale the 95%-CI will be displayed.
 
95%-Hodges-Lehmann-CI in case a GLMM-approach fails.

---------------------------	--

Sensitivity analysis of selected secondary endpoints	
In case of a relevant discrepancy between the sample size of the FAS and the PP population, a sensitivity analysis will be performed on the per protocol (PP) population, which will include data from subjects being compliant with the protocol.
 
The following rule is applied:
 
If the sample sizes of the FAS and PP populations differ by at least 10%, the following endpoints will be analysed on the basis of the PP population.
 
 
1) Proportion of subjects who achieve an increase of 2 mins from baseline in IELT in the 3% benzocaine condoms compared to the standard NRL condom.
 
2) Proportion of subjects who achieve an increase of 3 mins from baseline in IELT in the 3% benzocaine condoms compared to the standard NRL condom.
 
3) Proportion of subjects who achieve an increase of 4 mins from baseline in IELT in the 3% benzocaine condoms compared to the standard NRL condom.
 
4) Proportion of subjects who achieve an increase of 2 mins from baseline in IELT in the 5% benzocaine condoms compared to the standard NRL condom.
 
5) Proportion of subjects who achieve an increase of 3 mins from baseline in IELT in the 5% benzocaine condoms compared to the standard NRL condom.
 
6) Proportion of subjects who achieve an increase of 4 mins from baseline in IELT in the 5% benzocaine condoms compared to the standard NRL condom.
 
 
Clinically relevant differences between the results of the FAS and the PP analysis are highlighted and discussed.

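### SAP 12.12 gives an unpaired 2x2 odds ratio and interval that conflicts with the mixed-model odds ratios in SAP 11.4 and does not fit a crossover

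*SAP*

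**What the plan says.** Two parts of the SAP describe how odds ratios are obtained.

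- **SAP 11.4, For secondary endpoints** (and Protocol 9.5.2.1). The 2-, 3- and 4-minute responder endpoints use a binomial GLMM with treatment and period as fixed effects, baseline IELT as covariate and subject as random effect. PGIC uses a multinomial GLMM with treatment, period and random subject. Each condom comparison is to be "expressed as an odds ratio, with an associated 95% CI and p-value".
- **SAP 12.12, Confidence intervals.** "This calculator uses the following formulae to calculate the odds ratio (or) and its confidence interval". The estimate is ad/(bc), and the standard error of its log is sqrt(1/a + 1/b + 1/c + 1/d). The cells are counts of joint presence or absence of two things called A and B; for example, "a is the number of times both A and B are present". Neither letter is defined.

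The rule for means in 12.12 gives way to anything stated elsewhere. The rule for odds ratios has no such exception and is limited only to suitable cases. SAP 12.3 repeats that the comparison with the standard "condom will be expressed as an odds ratio, with an associated 95% CI" and does not name the source of the interval.

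The output shells follow the same split. In SAP 19.2 the GLMM mock table has coefficient, SE, DF, t and p but no odds ratio, and a separate mock table holds the odds ratio and its limits. In SAP 19.4, Tables 14.2.2.6 and 14.2.2.16 (descriptive statistics and odds ratio) are listed apart from Tables 14.2.2.7 and 14.2.2.17 (GLMM results).

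**The concern.** The responder and PGIC comparisons are the only odds ratios in the plan, so the 12.12 formula has no other stated use. A programmer filling the odds-ratio tables could reasonably take it as the instruction. It is a formula for independent observations, whereas every man in this trial is to use all three condoms.

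The result would be an odds ratio and interval that do not belong to the model whose p-value is reported in the companion table. Depending on how A and B are read, the interval is either not about treatment at all or is too wide. SAP 17 lists all six responder comparisons (three thresholds, two condoms) among the topline results chosen to support the primary endpoint, so the mismatch would be visible early.

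**Working it through.** **The plan's own figure.** Inputs from SAP 12.7: SD 7.1 minutes, within-subject correlation 0.5, difference 2 minutes, two-sided 5%, 90% power.
- SD of a paired difference = 7.1 × sqrt(2 × (1 − 0.5)) = 7.1.
- The normal approximation gives 133. The exact paired t-test gives 135 (power 0.901), and 135 / 0.9 = 150. The stated 135 and 150 are reproduced.

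**Assumptions added.** The documents give no responder rate and no correlation between responder indicators. I assume normal changes from baseline and the same 0.5 correlation between baseline and each period. The change then has SD 7.1. Two changes that share a baseline have covariance 7.1² × (1 − 0.5) and variance 7.1² each, so their correlation is 0.5.

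**Reading 1: A and B are one man's responses on two condoms. No treatment effect, n = 135.**
- 2-minute threshold: responder rate = 1 − Φ(2/7.1) = 38.9% on each condom.
- Expected cells: a = 31.0, b = c = 21.5, d = 60.9.
- ad/(bc) = 4.07 from unrounded cells.
- SE = sqrt(1/31.0 + 2/21.5 + 1/60.9) = 0.376. The 95% CI is 4.07 × exp(±1.96 × 0.376) = 1.95 to 8.51.
- 3-minute threshold: 4.16 (1.94 to 8.95). 4-minute threshold: 4.30 (1.92 to 9.62).
- With a true 2-minute shift (50% against 38.9%), the 2-minute value is 4.08. The quantity barely responds to treatment.

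Range of the null value over the assumed correlation between changes, for responder rates of 20% to 50%:

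| Correlation of changes | ad/(bc) |
|---|---|
| 0 | 1.0 |
| 0.3 | 2.2 to 2.5 |
| 0.5 | 4.0 to 4.7 |
| 0.7 | 8.7 to 10.6 |

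A different assumption is that the responder indicators themselves correlate at 0.5. With 30% responders:
- a = 135 × (0.09 + 0.105) = 26.3
- b = c = 135 × (0.21 − 0.105) = 14.2
- d = 135 × (0.49 + 0.105) = 80.3
- ad/(bc) = 10.5 (95% CI 4.5 to 24.8)

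**Reading 2: A is the condom and B the response.**
- With no effect the odds ratio is 1, as it should be.
- Unpaired SE = sqrt(2 / (135 × 0.389 × 0.611)) = 0.250. Allowing for pairing, it is 0.205. The ratio is 1.22.
- A nominal 5% test then has type I error 2 × (1 − Φ(1.96 × 1.22)) = about 1.7%.
- With a true 2-minute shift the marginal odds ratio is 1.57. The unpaired interval is 0.97 to 2.55 and the paired one 1.06 to 2.33.
- If the responder indicators correlate at 0.5, with 50% against 30% responders, the SEs are 0.255 and 0.180. The ratio is 1.41.

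The paired interval here is for the marginal odds ratio. A random-subject model can target a different quantity: in the same 2-minute example the ratio of discordant pairs is 1.97, against 1.57. So under Reading 2 even the point estimate need not match the GLMM.

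**PGIC.** SAP 11.4 analyses seven categories, and its example of collapsing still leaves three. A four-cell formula needs two, and the SAP defines no such split.

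**The case against.** The strongest reply is that 11.4 is specific and 12.12 is generic. SAP 11.4 and Protocol 9.5.2.1 name the model for each endpoint, while 12.12 names no endpoint, applies only where suitable, and reads like text carried over from a general source. A reader might infer that the SAP replaces the GLMM with a 2x2 table; the documents do not support that. What they show is two rules with no order of precedence. The reply does not dispose of the conflict, because the odds-ratio rule makes no exception for other sections and the table shells keep odds ratios apart from GLMM results.

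A reader might also infer that the cell definitions themselves make this an agreement measure between condoms. They do not, because A and B are undefined. The odds-ratio mock table labels its first row as treatment A against C, which points towards a treatment contrast and hence Reading 2. Under that reading there is no spurious effect, and the error is conservative.

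Finally, a null odds ratio near 10, or an SE 41% too large, might be taken as the expected size. Both need a correlation of 0.5 between responder indicators, which the plan does not state. Its 0.5 is for IELT in minutes.

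**Conclusion.** The conflict is real and should be fixed; it is not critical. SAP 12.12 supplies an unpaired rule for odds ratios that SAP 11.4 obtains from a model with a subject effect, and neither reading of 12.12 yields the interval of the GLMM odds ratio.

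- Under Reading 1, the null value is about 4 with the plan's 0.5 carried through a bivariate-normal model, and about 10 under the stronger assumption on responder indicators with 30% responders. Both intervals exclude 1.
- Under Reading 2, the SE is about 22% too large (41% under the stronger assumption). This costs precision but does not inflate false positives.

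The sizes depend on normality, equal correlations including baseline, and complete data on 135 men. The existence of the conflict depends on none of these.

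Nothing here supports an inference that the trial's main claim is at risk. The affected endpoints are secondary and unadjusted for multiplicity, the SAP overview marks them as non-confirmatory, and the primary comparison does not use an odds ratio.

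**What to change.** - Delete the 2x2 odds-ratio formula, its cell definitions and its standard error from SAP 12.12.
- State there that every odds ratio, 95% CI and p-value for the responder and PGIC endpoints comes from the treatment contrast of the GLMM in SAP 11.4.
- Fill the odds-ratio mock table in SAP 19.2, and the planned odds-ratio tables in SAP 19.4 such as 14.2.2.6 and 14.2.2.16, from that model, and say so in the shells.

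I would not add the matched-pair ratio b/c as a fallback. It drops period, baseline IELT and men with incomplete pairs. The bullets in 12.12 also define b as A present and B absent, whereas the printed table puts b where B is present and A absent, so the ratio could come out inverted. The SAP overview already names an alternative to the GLMM.

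The cost is SAP wording and table shells before database lock. No data collection changes, and the planned model already gives the interval.

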Subjects will attend the clinical site on 5 occasions: one screening visit, three assessment period visits and one follow-up visit. Screening includes a 4-week baseline period, which allows the subject and his partner to familiarise themselves with the use of the stopwatch method and completing IELT diaries. Eligible subjects will return to the clinical site, where they will be randomised and receive the first of the three condom types (according to the randomisation schedule). Subjects will be provided with 8 condoms per condom type. The process will be repeated until all three condom types have been used. The follow-up visit will occur within 7 days after the completion of the final condom assessment period. At least a 3-day washout period, where no test condom will be used, is required before subjects attend the clinical site for visit 3 and visit 4. The 3-day washout period is to mitigate the effects on any residual benzocaine across condom types.

The investigation design is outlined in the schematic below (Figure 3-1).

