### **Overall proportion of clinical failure event**

$$Proportion \pi = \frac{n_{CF}}{N} \cdot 100$$

for  $n_{CF} = \text{absolute number of clinical breakage or clinical slippage of condom (defined by ISO 29943-1)}$   
 $N = \text{total number condom usage}$

Note: The proportions are given in percent.

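### The formula printed as the Wilson score interval in SAP 12.12 has c²/(4n) under the root instead of c²/(4n²), so proportion CIs coded as printed are at least about 2.2 times too wide

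*SAP*

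**What the plan says.** SAP section 12.12 sets out the interval methods. For proportions it says: "The confidence intervals for the proportion values are calculated according to the Wilson Score method". It then adds: "The following calculation method is used for this purpose", followed by a formula. With p for the observed proportion, the formula reads

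CI = [ p + c²/(2n) ± c·√( p(1−p)/n + c²/(4n) ) ] / (1 + c²/n),

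where c is the standard normal quantile at 1 − α/2.

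The formula is therefore presented as the calculation itself and not as background. Nothing else in either document gives the term differently or names a software routine for this interval. SAP section 13 says that the SAS output is based on the SAP and is checked by a quality-control person. The overview table that follows SAP section 18 lists 95% confidence intervals in the rows for the 2-, 3- and 4-minute responder proportions.

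**The concern.** The method named and the formula prescribed are not the same thing. With n in place of n² in the last term, the quantity added under the root is larger than the binomial variance it is meant to adjust, whatever the proportion. The result is not a 95% interval and is not confined to 0 to 100%.

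The responder proportions are secondary endpoints and part of the topline results in SAP section 17. If a programmer follows the SAP literally, any interval printed beside those proportions will badly overstate the uncertainty, and at low or high response rates it will include impossible values. If the programmer uses a standard Wilson routine instead, the limits will be right but will not agree with the formula in the SAP.

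**Working it through.** The documents state no numerical interval for a proportion, so there is no planned figure to reproduce. The check compares the printed formula with the Wilson interval.

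**Inputs**
- c = 1.96, c² = 3.8415. The quantile at 1 − α/2 is given with the formula. The level is 95%: the odds-ratio paragraph of the same section says "for a confidence level of 95%, the type I error is" 0.05.
- n = 135 to 150. SAP 12.7: "A sample size of 135 subjects will be sufficient to detect a difference of 2 minutes" and "Allowing for a dropout rate of 10%, 150 subjects will be randomized" (135/0.9 = 150).
- Observed proportion p: the documents give no expected value, so the whole range from 0% to 100% is shown as an assumption.

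**Which term is right.** The Wilson limits are the values π that solve (p − π)² = c²π(1 − π)/n. Collecting terms:

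(1 + c²/n)π² − (2p + c²/n)π + p² = 0.

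The roots are [p + c²/(2n) ± √D]/(1 + c²/n), with

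D = (p + c²/(2n))² − (1 + c²/n)p² = c²·[ p(1−p)/n + c²/(4n²) ].

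So the centre and the divisor in the SAP are correct, and the last term needs n².

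**Worked case, n = 150, p = 5%**
- p(1−p)/n = 0.0475/150 = 0.0003167
- c²/(4n) = 0.0064024; c²/(4n²) = 0.0000427
- Centre: 0.05 + 0.012805 = 0.062805. Divisor: 1.02561.
- As printed: 1.96·√(0.0003167 + 0.0064024) = 0.1607, giving (0.0628 ± 0.1607)/1.0256 = −9.5% to 21.8%.
- Wilson: 1.96·√(0.0003167 + 0.0000427) = 0.0372, giving 2.5% to 9.8%.
- Ratio of widths: 0.1607/0.0372 = 4.3.

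**Across the range, n = 150**

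| p | As printed | Wilson | Width ratio |
|---|---|---|---|
| 0% | −14.0% to 16.5% | 0.0% to 2.5% | 12.2 |
| 1% | −13.2% to 17.6% | 0.2% to 4.2% | 7.7 |
| 5% | −9.5% to 21.8% | 2.5% to 9.8% | 4.3 |
| 10% | −5.0% to 27.0% | 6.2% to 15.8% | 3.3 |
| 30% | 13.6% to 47.4% | 23.2% to 37.8% | 2.3 |
| 50% | 32.8% to 67.2% | 42.1% to 57.9% | 2.2 |
| 90% | 73.0% to 105.0% | 84.2% to 93.9% | 3.3 |

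At n = 135 the ratios are 11.6 (0%), 7.5 (1%), 4.3 (5%) and 2.2 (50%). The Wilson column agrees with a standard software implementation at 0/150, 3/150 and 75/150.

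**Why a larger sample does not help.** The width ratio is √{[p(1−p) + c²/4] / [p(1−p) + c²/(4n)]}. Here c²/4 = 0.96, while p(1−p) never exceeds 0.25. At 50% the ratio tends to √(1.2104/0.25) = 2.2 as n grows. At 0% or 100% it equals √n.

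**Out-of-range limits.** The lower limit is negative for p below about 15% at n = 150 (about 16% at n = 135). By symmetry the upper limit passes 100% for p above about 85% (about 84%).

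**Coverage.** Exact binomial coverage of the printed interval exceeds 99.99% at true proportions of 5%, 10%, 30% and 50%, for both n = 135 and n = 150, against a nominal 95%.

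**The case against.** Four arguments limit the point.

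1. **The exponent may have been lost in reading.** The whole difference is one superscript in a nested fraction, in text extracted from a PDF. Other symbols in the same section look damaged: the rounding brackets in the Hodges-Lehmann description seem to be missing. This cannot be excluded. Against it, every squared c in the same formula survived, including the one directly above the denominator at issue. The source page settles it.

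2. **The reach is narrow.** A reader might infer from the general wording of 12.12 that every percentage in the report is affected. The documents do not support that. SPQ items get counts and percentages only (12.3 and the overview table). The clinical failure rate, whose denominator is "total number condom usage", gets descriptive statistics, counts and percentages without a CI. Adverse events are planned as counts and percentages. The PGIC interval in 12.3 is for an odds ratio. Section 11.1 asks only for frequencies of categorical variables, and the mock count tables have no CI columns. Even for the responder proportions, the only interval that 12.3 spells out is for an odds ratio. That a single-proportion interval will also be produced is an inference from the overview table. This argument stands, and it limits the point to intervals actually produced under 12.12.

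3. **Plots and quality control.** It would be tempting to say that charts will carry wrong error bars, or that a correct Wilson interval would be rejected at quality control. The planned bar charts show IELT and EMSEX, not proportions. Section 13 describes a risk-based control whose observations are implemented and documented, so a rejection is conjecture.

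4. **The method is correctly named.** A programmer who relies on the name will get the right limits, and negative limits would be noticed. This makes the harm conditional but does not make the formula correct. Between about 16% and 84% the error produces no impossible value that would reveal it.

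**Conclusion.** The formula as it stands is wrong. It is not the Wilson interval, and if coded literally at n = 135 to 150 it gives intervals from about 2.2 times too wide (at 50%) through 4.3 times (5%) and 7.5 to 7.7 times (1%) to about 12 times (0% or 100%).

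The consequence rests on three conditions: that the source page shows the same term, that the formula is coded as printed, and that a single-proportion interval is reported. The 2-, 3- and 4-minute responder proportions are the most plausible case. The primary mixed-model comparison, its p-value and interval, the model-based odds ratios and the sample size are all untouched. The point concerns descriptive precision and an internal contradiction in a controlled document, and it should be corrected because correction is almost free.

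**What to change.** Check the exponent on n against the source page of SAP 12.12. If the page shows c²/(4n), replace it with c²/(4n²). Alternatively, delete the formula and cite the Wilson option of SAS PROC FREQ, BINOMIAL(CL=WILSON). It would help to state in the same edit which proportions receive this interval, since section 12.3 and the overview table leave that open.

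The SAP's version-control note requires changes after the final version to be documented as an amendment, so the cost is one short amendment, best made before analysis. Design, data collection and the primary analysis do not change.
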